10.3. Unanticipated Problems, Adverse Events, Serious Adverse Events

Unanticipated Problems:

An unanticipated problem is any incident, experience or outcome that meets all three OHRP criteria (1) unexpected (in severity, specificity, frequency, or nature), (2) related or possibly related to the research, and (3) suggests the research places subjects or others at greater risk than previously known or recognized. Only a subset of adverse events will meet criteria for unanticipated problems.

Adverse Event (AE) Definitions:

An AE is any untoward medical occurrence in a patient or clinical investigation subject administered a pharmaceutical product and that does not necessarily have a causal relationship with this treatment. An AE can therefore be any unfavorable and unintended sign (including an abnormal laboratory finding), symptom or disease temporally associated with the use of a medicinal product whether or not related to the medicinal product. In clinical studies, an AE can include an undesirable medical condition occurring at any time, including baseline or washout periods, even if no study treatment has been administered. A treatment-emergent adverse event (TEAE) is an AE that occurs after the first administration of any study drug. The term study drug includes any Sage Therapeutics investigational product, a comparator, or a placebo administered in a clinical trial.

Serious Adverse Events (SAE) Definition:

An SAE is any untoward medical occurrence that at any dose:

- Results in death
- Is immediately life-threatening (Note: The term “life-threatening” refers to an event in which the subject was at risk of death at the time of the event; it does not refer to an event which hypothetically might have caused death if it were more severe.)
- Requires inpatient hospitalization or prolongation of existing hospitalization
- Results in persistent or significant disability or incapacity
- Results in a congenital abnormality or birth defect

An SAE may also be any other medically important event that, in the opinion of the Investigator, may jeopardize the subject or may require medical intervention to prevent one of the outcomes listed above. (Examples of such events include allergic bronchospasm requiring intensive treatment in an emergency room or convulsions occurring at home that do not require an inpatient hospitalization).

Grading the Severity of Adverse Events and Events of ‘Special Interest’:

We will employ the grading scale adopted by the UNC IRB to grade and report AEs. Adverse events will be classified according to severity as either mild, moderate, or severe.

Mild AE: is defined as having no effect on activities of daily living, such as transient lightheadedness or sweating with venipuncture; headache; mild skin irritation; or something of equal significance that requires no medical intervention and is of marginal clinical relevance.

Moderate AE: would be associated with temporary (minutes to a few days) disruption in activities of daily living, such as temporary loss of consciousness with venipuncture; worsening of migraines or headache that require bed rest; an increase in depressive symptoms above baseline of more than five points on the HAM-D; dizziness that precludes ambulation; or something of equal significance.

Severe AE: would include any event that acutely threatens the patient’s health, is life-threatening, or potentially permanently disabling, or an event of equal significance.

It is important to distinguish between serious and severe AEs. Severity is a measure of intensity whereas seriousness is defined by the criteria under Section 10.3. An AE of severe intensity may not be considered serious.

The following events are considered AESIs (Adverse Events of Special Interest) and should be reported on the AESI form within 72 hours.

- Excessive sedation
- Loss of consciousness
- Any sedation-related AE that leads to dose reduction, interruption, or termination

If the AESI also qualifies as an SAE an SAE form should be submitted per the guidelines above.

Relatedness Definition:

The Investigator must make the determination of relationship to the study drug for each AE (not related or related). The Investigator should decide whether, in their medical judgment, there is a reasonable possibility that the event may have been caused by the drug intervention. If no valid reason exists for suggesting a relationship, then the AE should be classified as “not related.” If there is any valid reason, even if undetermined, for suspecting a possible cause-and-effect relationship between the investigational product and the occurrence of the AE, then the AE should be considered at least “possibly related.”

Not Related: No relationship between the experience and the administration of study drug; related to other etiologies such as concomitant medications or subject’s clinical state.

Possibly Related: A reaction that follows a plausible temporal sequence from administration of the study drug and follows a known response pattern to the suspected study drug. The reaction might have been produced by the subject’s clinical state or other modes of therapy administered to the subject, but this is not known for sure.

Probably Related: A reaction that follows a plausible temporal sequence from administration of the study drug and follows a known response pattern to the suspected study drug. The reaction cannot be reasonably explained by the known characteristics of the subject’s clinical state or other modes of therapy administered to the subject.

If the relationship between the AE/SAE and the investigational product is determined to be “possible” or “probable”, the event will be considered related to the investigational product for the purposes of expedited regulatory reporting. AEs will be reported per Sage Therapeutics guidelines as “related” or “not related”.

Expectedness Definition:

The PI will be responsible for determining whether an adverse event is expected or unexpected. An AE will be considered unexpected if the nature, severity, or frequency of the event is not consistent with the risk information previously described for the study intervention.

AE and SAE Assessment, Follow-up Procedures:

The study coordinator or research nurse will monitor side effects and AEs every two hours when the patient is awake and receiving the infusion. Adverse events forms will also be completed after each EEG session and will include the assessment of EEG-related AEs, including discomfort and irritation from the EEG net and electrode gel. Side effects consistent with moderate or severe AEs or that are troublesome to the subject will also be immediately reported to the inpatient unit nurses and to [name], who will be responsible for determining the next course of action, which might include slowing or discontinuing the infusion or discontinuation of the subject from the study. [name] will review all protocol data monthly, including enrollment and retention statistics and aggregate reports of side effects/AEs. As the contact PI, [name] will be the one responsible to report all AEs reported as severe to the IRB within one week. The study sponsor will be notified of any study modifications or suspension imposed by the local IRB in response to an AE. Finally, it should be noted that the subjects will be hospitalized on an inpatient unit during the entire administration of BRX and will not be discharged until clinically cleared by the physician.

Reporting and Documentation Procedures:

All SAEs (regardless of causality) will be recorded from the signing of the consent form(s) until the final visit of the study for that subject. Serious adverse events occurring after the subject's final study visit should be reported to the Sponsor or Sponsor's designee only if the investigator considers the SAE to be related to study drug.

All SAEs must be reported to Sage Therapeutics, or designee, immediately. A written account of the SAE must be sent to Sage Therapeutics within 24 hours of the first awareness of the event by the Investigator and/or his/her staff to the IQVIA email address: [contact]. The Investigator must complete, sign and date the SAE report form, verify the accuracy of the information recorded on the SAE report form with the corresponding source documents, and send a copy to Sage Therapeutics, or designee.

Additional follow-up information, if required or available, must be sent to Sage Therapeutics, or designee, within 24 hours of receipt; a follow-up SAE form should be completed and placed with the original SAE information and kept with the appropriate section of the study file.

Sage Therapeutics, or designee, is responsible for notifying the relevant regulatory authorities of certain events. It is the Principal Investigator's responsibility to notify the IRB of all SAEs that occur at his or her site. Investigators will also be notified of all suspected, unexpected, serious, adverse reactions (SUSARs) that occur during the clinical study or from other studies with brexanolone. Each site is responsible for notifying its ethics committee of these SUSARs.

Participant Notification of New Information:

Corrective actions to be considered in response to New Safety Information include:

- Modification of inclusion or exclusion criteria to mitigate the newly identified risks.
- Implementation of additional safety monitoring procedures

- Suspension of enrollment of new participants or halting of study procedures for enrolled participants.
- Modification of informed consent documents to include a description of newly recognized risks.
- Provision of additional information about newly recognized risks to previously enrolled participants.

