7.1. Table of Events

Table 3: Schedule of Events

Study Procedure	Screening Period	Treatment Period/Inpatient Stay (Day 1 to Day 4)						Follow-up
		D-14 to 1	D1	D1	D1	D2	D3	
Visit Days		H0*	H4	H8	H28	H60	H72	D30 (±3d)
Hour								
Informed Consent	X							
SCID-5	X							
Demographics	X							
Medical History	X							
Height		X						
Body Weight		X						
Physical Examination ^a	X							
Drug and Alcohol Test ^b	X	X						
Pregnancy Test ^c	X	X						
Clinical lab assessments ^d	X							
ALLO blood sample ^e		X			X		X	
12-lead ECG ^f	X							
Vital Signs ^g	X	X	q4h (while awake) during infusion				X	
C-SSRS ^h	X	X					X	
HAM-D ⁱ	X	X	q4h (while awake) during infusion				X	X
SMDDS ⁱ		X	q4h (while awake) during infusion				X	X
EPDS ⁱ		X	q4h (while awake) during infusion				X	X
STAI (state Y-1) ⁱ		X	q4h (while awake) during infusion				X	X
SCS ⁱ		X	Q4h (while awake) during infusion				X	X
BIMF ⁱ		X					X	X
IDS-SR ⁱ		X					X	X
RRS-10 ⁱ		X					X	X
SHAPS ⁱ		X					X	X
STAI (trait Y-2) ⁱ		X					X	X
EEG Recording ⁱ		X	X	X	X		X	
RS Eyes Open/Closed (8min) ^{i,j}		X	X	X	X		X	

iMotion Recording ^{i,j}		X	X	X	X		X	
Semi-structured Interview ^{i,k}		X	X	X	X		X	
Brexanolone infusion				X				
Continuous pulse oximetry ^l				X				
Continuous HRV collection				X				
Adverse Events				q2h (while awake) during infusion		X	X	
Monitor for excessive sedation				q2h (while awake) during infusion				
Prior/Concomitant medications ^m	X	X				X	X	
Nonpharmacological interventions ⁿ	X	X				X	X	
Exit Interview								X
Compensation (total \$750)	\$50	\$100	\$100	\$100	\$100		\$100	\$200

AE= adverse event; ALLO= allopregnanolone; BIMF= Barkin Index of Maternal Functioning; C-SSRS = Columbia-Suicide Severity Rating Scale; D= Day; ECG= electrocardiogram; EEG= electroencephalogram; EPDS= Edinburgh Postnatal Depression Scale; HAM-D= Hamilton Depression Rating Scale; H=Hour; IDS-SR= Inventory of Depression Symptoms Self-Report; Q= every; RRS-10= Ruminative Responses Scale-10; RS= Resting State; SCID-5= Structured Clinical Interview for Diagnostic and Statistical Manual of Mental Disorders, Fifth Edition; SCS= State Complacency Scale; SHAPS= Snaith-Hamilton Pleasure Scale; SMDDS= Symptoms of Major Depressive Disorder Scale; STAI= State-Trait Anxiety Inventory;

* = All H0 procedures to be completed prior to dosing

a Full physical examination at screening. Symptom-directed physical examination may be conducted at subsequent time point

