7.3. Enrollment / Baseline (Day 0)

Refer to Tables 1 and 3 for schedule of procedures at Baseline. Procedures to be performed by the following personnel: PI, Study Coordinator, Research Nurse, and/or EEG technician.

Baseline (Hour 0)

- Subject will be admitted to UNC Hospital on a Monday or Tuesday morning. Prior to administration of drug intervention, the subject will undergo the following procedures:
 - Measure subject's height and weight, record, and submit to IDS to calculate drug dosage
 - Negative drug/alcohol and pregnancy test (if positive, subject will be withdrawn from the study)
 - Baseline blood sample to measure circulating allopregnanolone levels
 - Vital signs
 - Review of current concomitant medications and nonpharmacological interventions
- **First EEG recording:**

- EEG cap will be fitted by technician and electrodes filled with gel solution. Impedance will be measured to ensure proper adherence to scalp. Cap set-up will take approximately 20 minutes.
- Recording of 8-minute resting state EEG, eyes alternating open and closed at regular intervals.
- Cap will remain on the subject until the end of the Hour 8 session, so as not to disrupt the electrode placement over the course of the serial recordings. EEG will be recorded for 8-minute sessions at Hours 4 and 8 on Day 1 (not continuously throughout the day).
- **Self-Report measures:** Electronic versions of the following surveys will be administered: C-SSRS, EPDS; STAI (Y1&Y2); SCS; BIMF; IDS-SR; RRS-10; SHAPS.
- **Semi-Structured interview & iMotions Recording:** Facing a laptop equipped with a standard camera and microphone and iMotions Affectiva software, the subject will be administered a semi-structured interview about depressive symptoms and affect by study personnel. Interview questions will include the HAM-D and additional questions to assess the subject's experiences of enjoyment, guilt, and irritability. The interview and recording will last 10-20 minutes. A memory probe task will be completed, in which a subject will be asked to think of a sad event in her life and focus on that memory for 30 seconds while the laptop camera records her facial expressions. Then they will be asked to rate their emotional experience during that recall. This procedure will be repeated with a prompt to recall a happy memory from her life. Subjects will then be asked to come up with a word or phrase that can be used to recall each event during later recording sessions.

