9.2. Description of the Study Cohort

Descriptive methods to characterize the study cohort will include use of graphical figures, sample means, sample standard deviations, minimum, maximum, frequencies, and counts. Parameters examined will include age, parity, history of MDD, latency of onset, symptom rating scales (EPDS, HAM-D, anhedonia, rumination, complacency state scale, side effects), race, ethnicity, concurrent meds, concurrent anxiety disorder. For ordinal or ordered metric variables (symptom ratings), we will estimate means and confidence intervals. Mood measures will be used to see if the trajectory of treatment response is monotonic or whether it shows different trajectories by different symptom domains across individuals.

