The serious risks of BRX include excessive sedation and sudden loss of consciousness. Other risks are described in Section 10.1. These risks will be addressed by the progressive, stepped, infusion rate (with lower doses early), with the dose held rather than increased if the subject experiences dizziness or profound sedation. Patients will be monitored for the duration of the infusion and will also have consistent pulse oximetry to monitor and ensure adequate oxygenation. Additionally, possible side effects of BRX will be monitored with a Likert scale (1=Absent, 2=Mild, 3=Moderate, 4=Severe) that we have used in prior studies of BRX. If the participant reports side-effects of Moderate to Severe intensity, the study coordinator or research assistant will contact the study nurse to determine if adjustment or cessation of the infusion is required.

The UNC Hospitals Arousal Scale (see Table 5). will be administered every 2 hours during planned, non-sleep periods. If a score is equal to 3 on the Arousal Scale, the dose will be reduced by 50% and the inpatient prescriber or psychiatric on-call MD will be notified ([name]). If the score is less than or equal to 2 on the Arousal Scale, the infusion will be discontinued, and the MD will be contacted.

Table 5: UNC Hospitals Arousal Scale

5	Fully awake
4	Arouses easily
3	Arouses with tactile stimuli
2	Arouses to vigorous stimuli
1	Responsive to painful stimuli
0	Unresponsive

Time	Score	Time	Score
Hour 0:		Hour 32:	
Hour 2:		Hour 34:	
Hour 4:		Hour 36:	
Hour 6:		Hour 38:	
Hour 8:		Hour 40:	
Hour 10:		Hour 42:	
Hour 12:		Hour 44:	
Hour 14:		Hour 46:	
Hour 16:		Hour 48:	

Hour 18:		Hour 50:	
Hour 20:		Hour 52:	
Hour 22:		Hour 54:	
Hour 24:		Hour 56:	
Hour 26:		Hour 58:	
Hour 28:		Hour 60:	
Hour 30:			

Risks Associated with EEG: The possibility of rash will be addressed by monitoring the scalp for signs of irritation.

Risks Associated with phlebotomy: Subjects will be seated during the procedure to decrease the risk of fainting, and sterile technique will be employed to decrease the risk, albeit rare, of infection in the area of needle insertion.

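### No pre-infusion rating of the 1-4 side-effect scale is scheduled and no worsening rule is given, so its scores cannot separate symptoms present before drug from new or worsened ones

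*Combined protocol and SAP*

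**What the plan says.** **The scale.** Section 10.2 states that "possible side effects of BRX will be monitored with a Likert scale (1=Absent, 2=Mild, 3=Moderate, 4=Severe". It gives no item list and no time points for the scale. The same paragraph attaches an action to the score: "If the participant reports side-effects of Moderate to Severe intensity, the study coordinator or research assistant will contact the study nurse". The purpose of that contact is to decide whether the infusion needs changing or stopping.

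**The timing.** Section 10.3 says: "The study coordinator or research nurse will monitor side effects and AEs every two hours when the patient is awake and receiving the infusion". Table 3 has no row for the scale. Its Adverse Events row reads "q2h (while awake) during infusion", followed by two later marks. Section 7.3 lists the Hour 0 self-report measures as "C-SSRS, EPDS; STAI (Y1&Y2); SCS; BIMF; IDS-SR; RRS-10; SHAPS", and the side-effect scale is not among them. Nor is it in Table 1 or in the Hour 72 list in Section 7.6.

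**The analysis.** Section 9.2 includes "symptom rating scales (EPDS, HAM-D, anhedonia, rumination, complacency state scale, side effects" among the parameters to be described. Section 9.1 plans means and confidence intervals for pre-to-post infusion differences, where appropriate, and names symptom rating scales as one case.

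**Related safety records.** Section 10.3 adds: "Adverse events forms will also be completed after each EEG session and will include the assessment of EEG-related AEs". It defines a treatment-emergent event as one occurring after first dose, and it requires a relatedness judgement for each event. The arousal log in Table 5 starts with an Hour 0 entry.

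**The concern.** Some symptoms that a side-effect scale would be expected to pick up may exist before the drug is given. Women enter with a HAM-D of 20 or more and may be on stable psychotropics (Section 5.2). Table 1 describes the IDS-SR as covering lassitude and vegetative symptoms, while Section 10.1 lists sedation, somnolence and dizziness among brexanolone's effects. Tiredness and dizziness are used here as examples only, since the scale's items are not given.

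With no control arm, each woman's own pre-dose state is the only comparator. If it is not recorded on the same scale, the side-effect table mixes three groups: women whose symptom was there all along, women whose symptom worsened, and women in whom it is new. The third and second groups are what a reader of a tolerability table wants to see. The missing value cannot be recovered after the infusion starts.

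**Working it through.** The plan states no figure on this point, so the check sets its sections side by side.

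1. **Is a pre-dose rating scheduled?** Section 10.2 gives no times. Section 10.3 ties monitoring to the infusion. Tables 1 and 3 and Section 7.3 show no Hour 0 entry for the scale. Silence in Section 7.3 alone would be weak evidence, because its list also omits the SMDDS, which Table 1 schedules at baseline. The side-effect scale, however, is missing from every schedule.

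2. **What does the score measure?** The anchors run from absent to severe, so it records intensity and not change. Let *B* be the pre-dose rating and *R* a rating during infusion. A symptom is new or worsened when *R* > *B*:
   - *R* = 1: never emergent, whatever *B* is.
   - *R* = 2: emergent only if *B* = 1.
   - *R* = 3: emergent only if *B* = 1 or 2.
   - *R* = 4: emergent only if *B* = 1, 2 or 3.

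   Only *R* is collected, so every rating except 1 is undetermined.

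3. **Does the analysis need *B*?** The pre-post difference in Section 9.1 is post minus pre. For this scale the pre term is missing. No Hour 72 rating is scheduled either, so the post term is also unspecified.

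4. **Does another record supply *B*?**
   - *Adverse-event form after the first EEG.* It is pre-dose, since Table 3 says "All H0 procedures to be completed prior to dosing". The only content named for it is EEG-related, and it is not said to carry the 1-4 scale.
   - *Arousal log at Hour 0.* It covers arousal only, on a different 0-5 scale.
   - *IDS-SR at baseline.* It covers lassitude and energy on a different scale, and nothing links it to the side-effect ratings.
   - *Treatment-emergent definition.* It sorts events by onset and does not say how to treat a symptom that was present and then worsened.

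   None gives a graded pre-dose value. Elsewhere Section 10.3 does use the woman's own baseline: one example of a moderate event is a HAM-D rise of more than five points above it.

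5. **Illustrative size.** The documents give no prevalence of pre-dose symptoms. Let *p* be the assumed share of women with at least one moderate symptom on the scale before drug, and *n* = 12 (Section 5.1). The expected number is 12*p*, and the chance of at least one is 1 − (1 − *p*)^12.

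| *p* (assumed) | Expected women of 12 | Chance of at least one |
|---|---|---|
| 0.10 | 1.2 | 0.72 |
| 0.20 | 2.4 | 0.93 |
| 0.30 | 3.6 | 0.99 |
| 0.40 | 4.8 | 0.998 |

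These are women whose moderate rating could not be interpreted if the symptom persisted and was reported. They are not women shown to be misclassified. One woman is 1/12 = 8.3 percentage points of the cohort.

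**The case against.** The strongest reply is that the protocol has an attribution step. Adverse events may be recorded at baseline. Each is judged for relatedness, and the not-related category expressly allows for other medication and for the woman's clinical state, which are the two sources of concern here. Medical history, a neurological and mental status examination and a Hour 0 medication review also inform that judgement. A reader might otherwise infer that pre-existing symptoms will simply be counted as brexanolone side effects. The documents do not support that for adverse events.

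The reply stands for adverse-event reporting, but only in part for the scale. The relatedness judgement applies to events, while Section 9.2 summarises ratings. The judgement itself would also be better informed by a baseline. Under Section 10.3, an event with plausible timing and a known drug pattern is possibly related when clinical state might explain it but this is uncertain, and it then counts as related for expedited reporting.

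Two further replies have some force. Section 10.3 sets a frequency and does not say that the scale is used at no other time, so staff may rate it before dosing in practice. The marks after the infusion entry in Table 3 also suggest that adverse events are collected later. Both are reasons to write the time points down. Finally, this is a 12-woman descriptive study of EEG feasibility, and Section 9.1 plans differences only where appropriate. That limits the importance of the point without supplying the missing value.

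**Conclusion.** The point holds in a limited form. No pre-infusion rating of the 1-4 scale is scheduled and no worsening rule is given. The ratings summarised under Section 9.2 therefore cannot distinguish prior symptoms from emergent ones, and the Section 9.1 difference cannot be computed for this scale. This conclusion rests on the schedules as written and on the single-arm design. It does not depend on the assumed prevalence, which serves only as illustration.

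Two stronger readings should be avoided:

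- **That side effects are zero before drug by construction.** An unrated baseline is missing, not zero, and no section plans a before-and-after side-effect rate.
- **That the primary withdrawal count is inflated.** A moderate score prompts contact with the nurse. Any change to the infusion, or withdrawal under Section 6.7, then follows clinical judgement and not a cut-off on this scale. An effect on that count is possible but at most indirect, and its size cannot be derived from the documents.

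The change is worth making because it is cheap and must be in place before the first dose.

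**What to change.** - **Table 3:** add a row for the 1-4 side-effect scale with Hour 0 (before dosing), the existing two-hourly ratings during infusion, and Hour 72. The Hour 0 form can be completed with the adverse-event form already due after the first EEG.
- **Section 10.2:** attach the item list and state these time points. At Hour 0, word the form as current symptoms, since no drug has been given.
- **Section 9:** define an emergent side effect, item by item, as a rating above the woman's own Hour 0 value. Report the number of women with one alongside the raw ratings, and give Hour 72 minus Hour 0 as the pre-post difference. If the Hour 0 rating is missing, show the raw ratings and do not classify.

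The cost is two extra completions of a short form per woman, one table row and a few sentences. Dosing, the nurse-contact step and stopping rules are unchanged. An Hour 0 value separates prior symptoms from emergent ones. Without a control arm it still does not show that an emergent symptom was caused by the drug, and the report should say so.
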